## **4. Study Endpoints**

### 4.1. Safety Endpoints

Safety will be assessed by the investigator based on all AEs that occur during the 24 weeks (52 weeks for the long-term users) from the first treatment for all patients who have received at least 1 dose of Xeljanz® according to the local product document.

### 4.2. Efficacy Endpoints

The Mayo score or the partial Mayo score at week 8, 16, 24 and also 52 for the long-term users is assessed to see the remission, clinical response or mucosal healing. Investigator will perform the final efficacy evaluation of the drug into 4 categories based on the clinical impression plus Mayo score or partial Mayo score ('Improved', 'Unchanged', 'Aggravated', 'Not assessable').

If the patient does not complete the 24 or 52 weeks of treatment, relevant data should be collected based on the last assessment performed at the time of treatment discontinuation. The final efficacy evaluation will be determined by the investigator into 4 categories.

- Improved (Symptoms of ulcerative colitis have improved or showed adequate maintenance effect after taking Xeljanz®)
- Unchanged (Symptoms have not changed much since taking Xeljanz®)
- Aggravated (Symptoms have worsened after taking Xeljanz®)
- Not assessable

#### 1) Mayo score or partial Mayo score

Mayo score is based on a total score of 12 points by evaluating and calculating the four clinical evaluation criteria: Stool frequency, Rectal bleeding, Findings of endoscopy, and Physician's global assessment. Partial Mayo score is calculated by the sum of the remaining evaluations, except for the findings of endoscopy score.

#### 2) Mucosal healing (If endoscopy was done)

Mucosal healing is defined as an endoscopic score of 0 or 1.

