7.2.5.2. Demography and baseline characteristics

The following will be recorded on the CRF for each patient:

- Age: Record actual age of the patient at the time of enrollment. The age should be calculated by the date of birth.
- Sex: Check the box next to “male” or “female” on the CRF.
- Height: Record by unit of cm.
- Weight: Record by unit of kg.
- Herpes zoster vaccination: Record if the patient had received vaccine of herpes zoster: yes; no; unknown.
- Smoking: Record smoking status of the patient: ex-smoking; current smoking; non-smoking; unknown.
- Duration of the disease: Record the duration of disease since the date that the patient was initially diagnosed with UC.
- Severity of disease activity: Assess the severity (Mild, Moderate, Severe) by measuring Mayo or partial Mayo score and calculating the total score of 12 or 9 points based on clinical evaluation criteria: Stool frequency, rectal bleeding, findings of endoscopy, and physician's global assessment. Partial Mayo score excludes the findings of endoscopy. The severity for partial Mayo score is defined as 0-1 for remission, 2-4 for mild, 5-6 for moderate and 7-9 for severe disease activity.

- Previous UC treatments: Only record UC treatments received 6 months prior to the initiation of Xeljanz. Record name of the medication/therapy, route and duration of the administration, and overall response, if possible.
- Latent tuberculosis: Record if the patient has latent tuberculosis: yes; no; unknown.
- Renal impairment: Record if the patient has renal disorder: yes (severe/moderate/mild); none.
- Hepatic impairment: Record if the patient has hepatic disorder: yes (severe/moderate/mild); none.
- Other past/present diseases: Record “yes” or “no” for medical history. If “yes”, record adequate full name of the past or present disease according to the Medical Terminology Dictionary written by the Korean Medical Society. Past or present disease will be determined based on the date of the first dose of Xeljanz.

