7.3.3. Effectiveness evaluation

Effectiveness assessment will be performed by the accredited investigator in the Korean health care center. The investigator will perform the final effectiveness evaluation at baseline and after 8, 16 and 24 weeks of treatment based on the clinical impression and any of the commonly used effectiveness assessment criteria such as Mayo score or Partial Mayo score, and record the assessment results in each patient's CRF. 52nd week will be added for the long-term users. If the patient does not complete the 24 or 52 weeks of treatment, relevant data should be collected based on the last assessment performed at the time of treatment discontinuation. The final evaluation of the effectiveness will be determined by the investigator into 4 categories('Improved', 'Unchanged', 'Aggravated', 'Not assessable').

- Improved (Symptoms of ulcerative colitis have improved or showed adequate maintenance effect after taking Xeljanz)
- Unchanged (Symptoms have not changed much since taking Xeljanz)
- Aggravated (Symptoms have worsened after taking Xeljanz)
- Not assessible (Reason :)

If the overall effectiveness assessment is evaluated as 'Improved', 'Unchanged' or 'Aggravated', it is analyzed to be clinically significant. If the overall effectiveness assessment is evaluated as 'Not assessible', it is analyzed as not clinically significant. Among the 4 categories, 'Improved' is considered that the drug is effective. 'Unchanged' and 'Aggravate' are considered that there is a lack of effectiveness.

The Mayo score or the Partial Mayo score, which is referred in the effectiveness evaluation, are commonly used in actual medical practice. The Mayo score or the Partial Mayo Score at 8, 16 and 24 weeks(also 52 for the long-term users) will be assessed after the administration of Xeljanz, and Mayo Score measures the number of stool frequency, rectal bleeding, findings of endoscopy, and physician's global assessment. In total, based on the total score of 12 points, 0-2 points is rated as Remission, 3-5 as Mild, 6-10 as Moderate, and 11-12 as Severe. Partial Mayo Score is calculated by the sum of the remaining evaluations, except for the findings of endoscopy score. Based on the total score of 9 points, 0-1 is rated as Remission, 2-4 as Mild, 5-6 as Moderate and 7-9 as Severe.

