Remission is defined as Mayo score being less than or equal to 2 (in case of partial Mayo score, the score is less than or equal to 1) and other subscores not greater than 1 and rectal bleeding score of 0. Clinical response is defined as a decrease of Mayo score of more than 3 points and 30% from the baseline and a decrease of 1 or more in rectal bleeding score or rectal bleeding score of 0 or 1. Clinical response per partial Mayo score is a decrease of partial Mayo score of 2 or more and 30 % from the baseline and a decrease of 1 or more in rectal bleeding score or rectal bleeding score of 0 or 1. Clinical remission is defined as Mayo score being less than or equal to 2 and other subscores not bigger than 1. Endoscopic remission is endoscopic subscore of 0 and mucosal healing is defined as an endoscopic score of 0 or 1.

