#### **2.2. Study Design**

This is an open-label, non-comparative, non-interventional, prospective, and multi-center study conducted in Korean health care centers by accredited physicians (i.e., investigators). The study population will be adult patients with moderately to severely active UC who have had an inadequate response or intolerance to the basic treatments or biological agents. Clinical Severity of Ulcerative Colitis is classified as mild, moderate, or severe based on the Mayo score or partial Mayo score [Table 1].

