## Statistical Analysis Plan for rPMS

### 2.3. Study Population

#### 2.3.1. Inclusion Criteria

To be included in the study all patients will have received at least 1 dose of Xeljanz® for the treatment of the following indication as per local labelling:

- Moderately to severely active Ulcerative Colitis (UC) who have had an inadequate response or intolerance to the basic treatments or biological agents

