### 6.3. Efficacy Analyses

Efficacy analyses will be performed based on data of efficacy analysis set

- 1) Mayo index, Mayo score and partial Mayo score
  - Mayo index (stool frequency, rectal bleeding, physician's global assessment and finding of endoscopy), Mayo score or partial Mayo score at baseline, week 8 ( $\pm 15$  days), week 16 ( $\pm 15$  days), week 24 ( $\pm 15$  days) and changes from the baseline to last value will be presented in n, mean, SD, median, minimum and maximum. And changes from the baseline to last values will be tested by using paired t-test (or Wilcoxon signed rank test).
- 2) Mucosal healing (If endoscopy was done)
  - Mucosal healing at week 8 ( $\pm 15$  days), week 16 ( $\pm 15$  days), week 24 ( $\pm 15$  days) will be presented in frequency and percentage.
    - Achieved
    - Not achieved
- 3) Remission
  - Remission at week 8 ( $\pm 15$  days), week 16 ( $\pm 15$  days), week 24 ( $\pm 15$  days) will be

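### Mucosal healing is scored from the follow-up endoscopy alone, with no baseline condition, so the rate can count patients whose endoscopic subscore never changed

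*SAP*

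**What the plan says.** Protocol section 7.3.3 and SAP section 4.2, item 2, give the same rule. In the SAP, "Mucosal healing is defined as an endoscopic score of 0 or 1". In the protocol, "mucosal healing is defined as an endoscopic score of 0 or 1". The SAP item is headed "Mucosal healing (If endoscopy was done", and that is the only condition attached. SAP section 6.3, item 2, tabulates Achieved and Not achieved at weeks 8, 16 and 24. Section 6.4 repeats this for long-term users with week 52 added.

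Entry, in SAP section 2.3.1, is "Moderately to severely active Ulcerative Colitis (UC) who have had an inadequate response or intolerance to the basic treatments or biological agents". On grading, SAP section 2.2 says: "Clinical Severity of Ulcerative Colitis is classified as mild, moderate, or severe based on the Mayo score or partial Mayo score". Protocol section 7.2.5.2 notes that "Partial Mayo score excludes the findings of endoscopy". On the full score, protocol section 7.3.3 sets the bands: "0-2 points is rated as Remission, 3-5 as Mild, 6-10 as Moderate, and 11-12 as Severe".

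Both documents say that the study mandates no visit or activity. The efficacy set (SAP section 3.2) and the long-term efficacy set (section 3.4.2) require neither a baseline endoscopy nor an abnormal baseline subscore.

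**The concern.** The word healing implies a change from a worse starting state. The definition records only the state at follow-up. The two agree if every endoscoped patient starts at a subscore of 2 or 3, and nothing in the visible text ensures that.

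Two groups can then enter the numerator without evidence of healing:

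- patients already at 0 or 1 before the first dose who are still there at follow-up;
- patients with no baseline endoscopy, whose starting point is unknown.

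Mucosal healing is the only one of the three named outcomes (remission, clinical response, mucosal healing) that a patient rated moderate or severe can already satisfy at baseline. Clinical response requires a decrease from baseline. Remission requires a Mayo score of at most 2 or a partial Mayo score of at most 1, and a patient at 6 or more (partial: 5 or more) cannot already be there.

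What is at stake is how the healing percentage in the re-examination report is read. No test or comparison depends on it.

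**Working it through.** The documents state no healing rate, so there is no figure to reproduce. Two checks apply.

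**1. Can a patient rated Moderate already meet the definition?**

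Inputs: four subscores from 0 to 3 (Table 1 in both documents) and the full Mayo bands in protocol section 7.3.3.

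Example: stool frequency 2 + rectal bleeding 1 + endoscopy 1 + global assessment 2 = 6, which is Moderate. The endoscopic subscore is already 1. If it is still 1 at week 8, the patient is Achieved.

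The three non-endoscopic items have 64 combinations. The numbers totalling 3, 4, 5, 6, 7, 8 and 9 are 10, 12, 12, 10, 6, 3 and 1. To reach a full total of 6-10:

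- endoscopy 0 needs 6-9 from the other items: 10 + 6 + 3 + 1 = 20;
- endoscopy 1 needs 5-9: 12 + 10 + 6 + 3 + 1 = 32;
- endoscopy 2 needs 4-8: 12 + 12 + 10 + 6 + 3 = 43;
- endoscopy 3 needs 3-7: 10 + 12 + 12 + 10 + 6 = 50.

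The total is 145 combinations, of which 20 + 32 = 52 have an endoscopic subscore of 0 or 1. The highest full total is 9 with subscore 0 and 10 with subscore 1, both Moderate. These are possible score patterns, not patient frequencies. They show that the case can occur, not how often. On the partial score, 32 of 64 patterns total 5 or more, with the endoscopic subscore unrestricted or unknown.

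**2. How far could the rate move?**

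Among endoscoped patients, let q be the share starting at 0-1, s the share of those at 0-1 at follow-up, and h the healing rate among those starting at 2-3. Then:

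- reported rate = q·s + (1 − q)·h
- excess over h = q·(s − h)

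None of q, s or h is in the documents. With h assumed at 30%:

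| q | Rate, s = 90% | Rate, s = 100% | Excess (points) |
|---|---|---|---|
| 5% | 33% | 33.5% | 3 to 3.5 |
| 10% | 36% | 37% | 6 to 7 |
| 20% | 42% | 44% | 12 to 14 |

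At s = 90%, patients who started at 0-1 make up q·s divided by the reported rate: 0.045/0.33 = 14%, 0.09/0.36 = 25% and 0.18/0.42 = 43% of all Achieved.

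Over wider assumed ranges (q 5-30%, s 80-100%, h 20-50%) the excess runs from 0.05 × (0.80 − 0.50) = 1.5 points to 0.30 × (1.00 − 0.20) = 24 points.

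**The case against.** The definition is a status at a visit, the same in both documents, and remission is also defined without a baseline term. Clinical response is the endpoint built on change. SAP section 6.3, item 1, also summarises the endoscopy finding at baseline and at each time point, with change to the last value, so a reader will see how many patients had a baseline endoscopy and whether any started low. This stands in part. A score of 0-1 is a valid description of endoscopic state at follow-up. But those summaries do not cross-classify healing by baseline, and remission cannot already be met by a patient rated moderate or severe.

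Three stronger readings are tempting, and the documents do not support them.

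- *That these patients have nothing to heal.* Table 1 defines subscore 1 as mild disease, and 32 of the 52 patterns have subscore 1. Only subscore 0 is normal or inactive. Without a baseline endoscopy the starting point is unknown, not normal.
- *That the rate can only be biased upwards.* The sign of q·(s − h) depends on s exceeding h, which is plausible but assumed. Endoscopy is also optional. If it is done mainly in patients doing poorly, the net rate could be too low.
- *That the population is not selected towards endoscopic disease at all.* Entry for moderate to severe disease after inadequate response or intolerance selects in that direction without guaranteeing it. Entry also follows the local label, which is not available here. The supportable statement is that the visible text sets no endoscopic threshold.

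It is also fair that safety is the primary endpoint, that healing gets only frequencies and percentages, and that the SAP's factor analyses for efficacy use the investigator's effective rate instead.

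**Conclusion.** The point holds as a matter of interpretation. As written, a patient rated Moderate can meet the healing definition before the first dose and be tabulated as Achieved with no change. For patients without a baseline endoscopy, the table cannot show healing.

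The reported rate exceeds the rate among patients starting at 2-3 if those starting at 0-1 are more likely to be at 0-1 later. Under the assumptions above (30% true healing, 5-20% starting at 0-1, 90-100% of them staying there), the excess is about 3 to 14 points. The documents supply none of these inputs, and the real effect may be small in a moderate-to-severe population. The calculation also leaves aside selection in who is endoscoped.

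Type I error and power are not involved, because this is a descriptive secondary endpoint in a single-arm study. Severity is minor.

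**What to change.** In SAP section 4.2, item 2, section 6.3, item 2, and the repeat under section 6.4:

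1. Keep the protocol-defined proportion with a subscore of 0 or 1, and label it as endoscopic status among patients endoscoped in the visit window.
2. Break it down by baseline endoscopic subscore: 0-1, 2-3, not done. Give the number of patients in each row.
3. Base any statement about mucosal healing on the 2-3 row.

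This keeps the overall figure consistent with the protocol and drops no patient from the report. It needs no additional endoscopy, because SAP section 6.3, item 1, already uses the baseline endoscopy finding. Protocol section 7.7 allows the SAP to modify the plan and asks for a protocol amendment only for major changes to the primary endpoint, so SAP wording and one extra table classification are enough.

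The cost is a smaller and selected denominator for the healing rate, since endoscopy is optional at both time points, and probably a less favourable figure. The row counts should be shown so that this selection is visible.

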## **Statistical Analysis Plan for rPMS**

- Achieved
- Not achieved

3) Remission

Remission is defined as Mayo score being less than or equal to 2 (in case of partial Mayo score, the score is less than or equal to 1) and other subscores not greater than 1 and rectal bleeding score of 0.

- Achieved
- Not achieved

4) Clinical response

Clinical response is defined as a decrease of Mayo score of more than 3 points and 30% from the baseline and a decrease of 1 or more in rectal bleeding score or rectal bleeding score of 0 or 1. Clinical response per partial Mayo score is a decrease of partial Mayo score of 2 or more 30% from the baseline and decrease of 1 or more in rectal bleeding score or rectal bleeding score of 0 or 1.

- Achieved
- Not achieved

5) The final efficacy evaluation determined by the investigator

- Effective
  - Improved
- Not-effective
  - Unchanged
  - Aggravated

## **5. General Consideration**

### **5.1. Analysis Principles**

Statistical analysis will be conducted after database is locked and performed using SAS software version 9.4 or higher according to this Statistical Analysis Plan (SAP). If statistical analysis methods are changed, it will be described in the final clinical study report.

In case of statistical testing, two-sided tests will be conducted at a 5% significance level and the p-value of each test result will be presented in the summary table.

### **5.2. Handling of Missing and Incomplete Data**

#### **5.2.1. Handling of Missing Data**

If data are missing or if a subject decided to discontinue from the study, there will be no imputation applied except as specified in section 5.2.2. The impact of missing data will be evaluated as appropriate.

## **Statistical Analysis Plan for rPMS**

### 5.2.2. Handling of Missing and Incomplete Dates

Missing or incomplete dates will be handled by following rule:

	Missing	Imputation
Disease duration	YYYY	0 year
	MM	0 month
	YYYY/MM	No imputation
End date of treatment	'Taking Xeljanz®'	The last follow-up date

## 6. Statistical Analyses

### 6.1. Demographic and Baseline Characteristics

Demographic and baseline characteristics, past/present disease, concomitant medications, administration status for the study drug will be summarized with descriptive statistics.

#### 6.1.1. Demographic and Baseline Characteristics

- 1) Sex will be presented in frequency and percentage.
- 2) Age (year) will be presented in n, mean, SD, median, minimum and maximum. Also, frequency and percentage of each group categorized according to the distribution for age will be presented.
- 3) Geriatric subjects ( $\geq 65$  years) will be presented in frequency and percentage.
- 4) Height (cm) will be presented in n, mean, SD, median, minimum and maximum.
- 5) Weight (kg) will be presented in n, mean, SD, median, minimum and maximum.
- 6) Disease duration\* (month) will be presented in n, mean, SD, median, minimum and maximum. Also, frequency and percentage of each group categorized according to the distribution for disease duration will be presented.

\*The duration from when ulcerative colitis was first diagnosed until the day that first dose of Xeljanz® is taken.

Disease duration (month) = (Year of disease duration  $\times$  12) + Month of disease duration

- 7) Disease severity will be presented in frequency and percentage.
- 8) Latent tuberculosis will be presented in frequency and percentage.
- 9) Herpes zoster vaccination will be presented in frequency and percentage.
- 10) Smoking will be presented in frequency and percentage.

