7.7.4 Statistical consideration

For the safety and effectiveness outcome variables, the statistically significant differences for each classification group are statistically processed using the χ^2 test ($p \leq 0.05$). The incidence of each anomaly is presented with a 95% confidence interval. In order to analyze the factors affecting safety, a list of abnormal case expressions was prepared by the types of abnormal cases and by the background factors of the subjects (by gender, age and the presence or absence of accompanying diseases). Analyze the factors using a categorical data analysis method (Chi-square test, Fisher's Exact test). For statistically significant items, the pharmacological significances are described, and major adverse events, drug adverse reactions, and unexpected adverse events will be summarized in a table.

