## **Statistical Analysis Plan for rPMS**

- Occurrence status of adverse events by their seriousness [SAE]
  - Results in death
  - Is life-threatening
  - Requires inpatient hospitalization or prolongation of hospitalization
  - Results in persistent or significant disability/incapacity
  - Results in congenital anomaly/birth defect
  - Other important medical event
- [Non-SAE]
- Occurrence status of adverse events by action taken
  - Permanently discontinued
  - Temporary discontinued or delayed
  - Dose reduced
  - Dose increased
  - No change
  - Not applicable
- Occurrence status of adverse events by their causality assessment to Xeljanz®
  - Related to Xeljanz®: ① Certain  
② Probable/likely  
③ Possible  
⑤ Conditional/unclassified  
⑥ Unassessable/unclassifiable  
⑦ Not applicable
  - Not related to Xeljanz®: ④ Unlikely
- Occurrence status of adverse events by their other causality assessment (In case of 'Unlikely')
  - Disease under the study
  - Other diseases
  - Concomitant treatment-medication or non-medication
  - Other

3) Occurrence status of adverse events by demographic and other baseline characteristics

- The incidence of adverse events and 95% C.I will be presented by categorical variables of demographic and other baseline characteristics.
- To identify statistically significant difference in the incidence of adverse events by categorical variables of demographic and other baseline characteristics, Chi-square test ( $\chi^2$  test) or Fisher's exact test (if the expected frequency for each cell under 5 is more than 20%) will be performed.

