## **Statistical Analysis Plan for rPMS**

presented in frequency and percentage.

- Achieved
- Not achieved

4) Clinical response

- Clinical response at week 8 ( $\pm 15$  days), week 16 ( $\pm 15$  days), week 24 ( $\pm 15$  days) will be presented in frequency and percentage.
- Achieved
- Not achieved

5) Final efficacy assessment by the investigator

- Final efficacy assessment by the investigator classified as follows will be presented in frequency and percentage.

[Effective]

- Improved

[Not-effective]

- Unchanged

- Aggravated

6) Effective rate by demographic and other baseline characteristics

- Effective rate and 95% C.I will be presented by categorical variables of demographic and other baseline characteristics.
- To identify statistically significant difference in the effective rate by categorical variables of demographic and other baseline characteristics, Chi-square test ( $\chi^2$  test) or Fisher's exact test (if the expected frequency for each cell under 5 is more than 20%) will be performed.

7) Analysis of factors that affect the efficacy

- In the re-examination report, logistic regression of multivariate analysis will be performed and an odds ratio with 95% C.I and p-value will be presented to identify the factors that affect effective rate in demographic and other baseline characteristics.

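### The factor tests ignore the order of age, disease-duration and severity groups, and the logistic models do not say whether age, duration and weight enter as continuous terms

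*SAP*

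**What the plan says.** **Grouping.** SAP 6.1.1 item 2 says for age that "frequency and percentage of each group categorized according to the distribution for age will be presented". Item 6 says the same for disease duration: "frequency and percentage of each group categorized according to the distribution for disease duration will be presented". Neither item gives a number of groups, boundaries or a quantile rule. Item 3 adds a separate flag for patients aged 65 or over. Height and weight (items 4 and 5) are summarised only as continuous variables. Severity (item 7) is categorical, and its Mayo and partial Mayo bands are fixed in Protocol 7.3.3.

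**Testing.** SAP 6.2 item 3 states its purpose as "To identify statistically significant difference in the incidence of adverse events by categorical variables of demographic and other baseline characteristics". It uses the chi-square test or "Fisher's exact test (if the expected frequency for each cell under 5 is more than 20%) will be performed". SAP 6.3 item 6 applies the same pair of tests, with the purpose "To identify statistically significant difference in the effective rate by categorical variables of demographic and other baseline characteristics". Protocol 7.7.4 lists age among the background factors and names the same tests: "Analyze the factors using a categorical data analysis method (Chi-square test, Fisher's Exact test"). SAP 6.4 repeats these analyses in long-term users. No trend test is named in either document.

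**Modelling.** SAP 6.2 item 4 and 6.3 item 7 plan multivariable logistic regressions to find factors for AE incidence and effective rate. They do not list the covariates or say whether age, duration and weight enter as continuous terms or as groups.

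**The concern.** These analyses are meant to find patient factors that affect safety and effectiveness. Age and disease duration are collected as numbers, and severity is graded. Cutting a number into bands discards the variation within each band. A test on k unordered bands then spreads its sensitivity over k − 1 degrees of freedom instead of aiming it at a steady rise or fall, which is often the pattern of interest. A moderate gradient in AE risk with age could be missed when the data already collected would show it. The logistic models could make good the loss, but only if the ordered factors enter them suitably, and the SAP does not say so.

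**Working it through.** **Inputs from the documents.** Tests are two-sided at 5% (SAP 5.1). SAP 2.4 gives at least 600 patients and says that sample size calculations do not apply. Protocol section 5 equates 18 long-term users with 20% of those enrolled, which implies 18 / 0.20 = 90 patients. No power, AE rate, effect size or number of groups is stated, so there is no figure of the plan's own to reproduce.

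**Assumptions for the example.** The factor is normally distributed and has a linear effect. It is cut into k equal-sized groups. A 1-df test on the continuous factor has 80% power, so its noncentrality is λ = (1.960 + 0.842)² = 7.85.

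**Step 1: information kept by grouping.** With cut-points c_j at the normal quantiles and density φ, the mean of group j is m_j = k[φ(c_(j−1)) − φ(c_j)]. The fraction of information kept is e_k, the average of m_j². For k = 2, m = ±2 × 0.399 = ±0.798, so e_2 = 0.637.

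**Step 2: power.** The noncentrality after grouping is λ × e_k. The unordered test refers it to a noncentral chi-square with k − 1 df. The trend test, scored at the group means, uses 1 df.

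| k | e_k | λ × e_k | Unordered power | Trend power | Unordered loss vs continuous (points) | Unordered loss vs trend (points) |
|---|---|---|---|---|---|---|
| 2 | 0.637 | 5.00 | 60.8% | 60.8% | 19.2 | 0 |
| 3 | 0.793 | 6.23 | 60.1% | 70.4% | 19.9 | 10.3 |
| 4 | 0.861 | 6.76 | 57.3% | 73.9% | 22.7 | 16.6 |
| 5 | 0.897 | 7.04 | 54.3% | 75.6% | 25.7 | 21.3 |

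The last column is what a trend test recovers. The rest of the loss to the continuous test comes from the grouping and needs a continuous term.

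**Step 3: dependence on the reference power.** With 4 to 5 groups, the loss against a continuous test is 13 to 14 points when that test has 30% power, 20 to 22 at 50%, 14 to 16 at 95% and 6 to 7 at 99%. With 7 groups and 80% reference power it reaches 31.1 points.

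**Step 4: simulation with assumed AE risks and odds ratios** (4 and 5 groups, 2,000 runs per cell).
- N = 600, AE risk 30%, odds ratio 1.3 per SD: continuous 82–83%, unordered 63% (k = 4) and 58% (k = 5), a loss of 19 to 25 points.
- N = 90, AE risk 30%, odds ratio 1.8 per SD: about 70% against 43–44%, a loss of 26 to 28 points.
- N = 600, AE risk 20–40%: a loss of 3 to 12 points at odds ratio 1.5, and none at 1.8 or more.
- N = 90, AE risk 20–40%, odds ratio 1.2: a loss of 3 to 6 points.
- N = 600 with a U-shaped effect: the unordered test has 33–37% power and the linear test 7–8%, so the comparison reverses.

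**The case against.** **The tests are valid and fit the purpose of the study.** Chi-square and Fisher's exact tests hold their level and are the ones the protocol names. Protocol 7.7 says that evaluation rests mainly on summary displays. The primary interest, AE incidence with a 95% confidence interval (Protocol 7.7.1), is untouched. All of this stands, and it makes the point one of efficiency in secondary, exploratory analyses.

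**The logistic models may already do the work.** Nothing in SAP 6.2 item 4 or 6.3 item 7 says that age or duration enters as groups. That also stands, but nothing says they enter as continuous terms either.

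**A trend test can miss non-monotone effects.** This is true, so the planned tests should be kept beside it. For a factor with only two observed levels the two tests coincide. Severity may be such a factor, since the inclusion criterion admits moderate to severe disease.

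Three stronger readings are tempting but not supported:
- *The plan loses a fixed 20 to 25 points of power.* That range needs roughly 3 to 5 groups, a linear effect and a continuous comparator with about 50% to 80% power. The documents supply none of these.
- *Cut-points will be chosen after AEs are seen, which inflates false positives.* The SAP's wording points to the distribution of the factor itself, and quantile bands set that way do not inflate type I error. Inflation needs a choice guided by outcomes, which the SAP does not describe. If the smallest p-value were picked, simulated type I error would be about 13% over four quantile schemes and about 25% over nine decile splits. Those figures describe a practice the plan does not state. The dummy-table attachment listed in SAP section 8 may also hold bands; its content is not in the text available.
- *Weight and height are never examined.* The restriction to categorical variables applies to 6.2 item 3 and 6.3 item 6. The logistic models carry no such restriction.

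**Conclusion.** The point holds as a moderate, inexpensive improvement. The univariate factor tests ignore the order of age, duration and severity groups, and the covariate form in the logistic models is unstated. Under a linear effect, equal groups and 80% power for a continuous test, a trend test on 3 to 5 groups gains about 10 to 21 points over the unordered test. A continuous term gains about 20 to 26 points. These figures illustrate the mechanism and are not estimates for this study: sample size, AE rate, effect size and number of bands are either unstated or, for sample size, differ between SAP 2.4 and the figure implied by Protocol section 5. The loss is negligible for a large effect and reverses for a U-shaped one. The missing banding rule is a gap in detail. It is not evidence that cut-points depend on outcomes.

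**What to change.** 1. Keep the chi-square or Fisher results and the grouped rates with confidence intervals in SAP 6.2 item 3 and 6.3 item 6.
2. Add a Cochran-Armitage trend test for ordered factors (age bands, duration bands, severity), in its exact form where cells are sparse. Carry it into the long-term analyses of SAP 6.4.
3. In SAP 6.2 item 4 and 6.3 item 7, list the covariates and enter age, disease duration and weight as continuous terms.
4. In SAP 6.1.1, state a banding rule that does not depend on outcomes, for example quantiles plus the existing 65-year boundary. If the dummy tables already hold the bands, cite them in the SAP body.
5. SAP version 1.1 is dated 2 November 2022, after the planned end of data collection on 19 September 2022. Record when these choices were made relative to database lock. SAP 5.1 already provides for describing changes of method in the final report.

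The cost is some SAP text and a test option in the software, with no new data. There will be a few more exploratory p-values. The trend test is less sensitive to non-monotone effects, and the retained chi-square test covers those.
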